Research hypothesis

Ho: The change in the score of the IIEF-EF scale in patients with moderate erectile dysfunction³, treated with radial wave therapy, is equal to those who receive placebo therapy.

Ha: The change in the score of the IIEF-EF scale increases at least five points in patients with moderate erectile dysfunction treated with radial wave therapy, compared with the score of patients receiving placebo therapy.

Study population

Patients diagnosed with erectile dysfunction of vascular origin who are treated at the Boston Medical Group facilities in Bogotá.

Inclusion criteria

- 1. Men older than 18 years
- 2. Erectile dysfunction presents for more than 3 months in more than 50% of intercourse.
- 3. IIEF-EF score between 11 and 21.
- 4. Patient who agrees to enter the study through the signing of an informed consent.

Exclusion criteria

- 1. EHS score of 4
- 2. Bladder, prostate or colon cancer.
- 3. Patients with ED of psychological origin.
- 4. Patients with spinal cord injury.
- 5. Patients with anticoagulant use.
- 6. Patients with sickle cell anemia.
- 7. Patients with clinical suspicion of hypogonadism (AMS greater than 36, Annex 1).
- 8. Patients with infections or active lesions of the penis or pubic area.
- 9. Patients with ED secondary to drug treatment (antiandrogenic therapy, antidepressants, use of corticosteroids, antiparkinsonians, antipsychotics).
- 10. Radical prostatectomy or other radical pelvic surgery.
- 11. Antecedents of pelvic radiotherapy.
- 12. Patients with penile implant.
- 13. Endocrine diseases that occur with ED: acromegaly, gigantism, Addison's disease, hyperprolactinemia, androgenic deficiency.
- 14. Patients with neurological diseases (Parkinson's, CVD, dementia of any origin)

³ For this study moderate erectile dysfunction is considered a score on the IIEF-EF scale from 11 to 21, which includes the mild to moderate and moderate categories.

Sample size

Assuming that the placebo plus drug group has an average change in the score of the IFE-EF scale of 5 points and that the new wave therapy must have an additional change of at least 5 points to be considered clinically relevant, for a power of 80% and a one-tailed level of significance of 97.5%, with a standard deviation of 8 points, a sample size of 33 patients was estimated for each group. Adjusting for a percentage of losses of 20%, the size per group is 40 patients, for a total of 80 patients in the study. These calculations were performed in Stata 15.1®.

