Interventions

Each patient will be assigned randomly to one of the following groups:

- Arm 1 (Radial wave therapy + oral treatment): 6 radial waves' sessions. A weekly session of radial waves will be applied with the following parameters: 6000 pulses at 1.5-2.6 bar (depending on patient tolerance), with a frequency of 17Hz, the frequency should increase to 22HZ the first 500 impulses to create mild anesthesia in the area; in all the sessions of radial waves, 4000 impulses will be distributed in the body of the penis in scanning technique and 2000 impulses in the perineal area, specifically in the ischiocavernosus and bilateral bulbo-sponge muscles. During the period of therapy application, patients will receive oral treatment with sildenafil 4 according to the patient's degree of affectation.
- Arm 2 (Placebo therapy + oral treatment): 6 sessions of placebo therapy. There will be a weekly session of placebo wave therapy, using the respective device to prevent the patient from receiving the radial wave. The same parameters of the "real" therapy will be used: 6000 pulses at 2.6 bar, with a frequency of 17 Hz; in all the sessions of radial waves, 4000 impulses will be distributed in the body of the penis in scanning technique and 2000 impulses in the perineal area. During the period of therapy application, patients will receive oral treatment with sildenafil 5 according to the patient's degree of affectation.

The radial waves will be administered with the Masterpuls MP50 device from Storz medical.

Primary Outcome

The primary outcome of this study is the difference in the average score of the IIEF-EF scale (Annex 3) in at least 5 points at the end of the treatment.

Secondary outcomes

- IIEF-EF score after one month of follow-up.
- Erection Hardness Score (EHS) at the end of treatment and one month follow-up: The EHS is a unique Likert scale and the version validated in Spanish (35) will be used, which has the following score, 0: The penis does not change in size or hardness; 1: The penis increases in size but does

⁴ This is the standard treatment.

⁵ This is the standard treatment

not become rigid; 2: The penis is rigid but not enough to penetrate; 3: The penis is rigid enough for penetration but not completely hard; and 4: The penis is completely hard or rigid (Annex 4).

- Change in the dose or use of sildenafil.
- Incidence of adverse events.

Safety

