The research subjects will be followed up one month after the end of the treatment. In the event that the patient cannot attend the follow-up, the respective scales will be sent to his e-mail so he can process them and return them by the same means; if after 3 days no response is received, a research assistant will call him and apply the questionnaires by telephone.

Statistical Analysis

A descriptive analysis of the individuals' baseline characteristics linked to each treatment arm will be made, estimating measures of central tendency and dispersion in the case of continuous variables, and measures of relative and absolute frequency for categorical variables.

To evaluate the effectiveness of the therapy, the change in the IIEF-EF scale will be compared at the end of the treatment with the baseline score for each of the arms, using parametric tests in case the

data present a normal distribution, or nonparametric tests otherwise. This same analysis will be done for the scores at the one-month follow-up.

For the EHS scale, the change in at least 1 point will be evaluated, in any of the established measurements. The association between the change in the score and the received treatment will be evaluated estimating the relative risk with its respective confidence interval.

The percentage of patients that decrease or discontinue the use of sildenafil in each group will be estimated, comparing the proportion between the groups at the end of the therapy scheme and the month of follow-up, using the Chi-square test.

The incidence of adverse events for each of the intervention groups will be estimated and the value between them will be compared using the Chi-square test.

In addition to the comparison between groups, stratified analyzes will be performed with multivariate regression models to determine how each intervention adjusted for covariates, such as comorbidities or additional treatments.

An interim analysis will be done once 60% of the total number of patients has completed the treatment (main outcome).

Expected impact

The main contribution of this study is for the scientific community and for patients with erectile dysfunction, by collecting scientific evidence of quality that allows to make a decision about the use of radial waves for the management of erectile dysfunction.

Ethical aspects

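### The alternative hypothesis and primary outcome state a gain of at least 5 points, but the sample size rests on a zero-difference null and the analysis has no 5-point margin, so rejecting Ho shows only a difference above zero

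*Combined protocol and SAP*

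**What the plan says.** Four places in the combined protocol and SAP bear on this.

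- **Research hypothesis.** Ho is that the change in patients "treated with radial wave therapy, is equal to those who receive placebo therapy". The alternative reads "Ha: The change in the score of the IIEF-EF scale increases at least five points in patients with moderate erectile dysfunction" given radial waves, "compared with the score of patients receiving placebo therapy". The comparison in the hypotheses is thus between arms.
- **Sample size.** The new therapy "must have an additional change of at least 5 points to be considered clinically relevant". The calculation assumes 80% power and "a one-tailed level of significance of 97.5%, with a standard deviation of 8 points, a sample size of 33 patients" per group, raised to 40 per group for 20% losses.
- **Primary Outcome.** It is "the difference in the average score of the IIEF-EF scale (Annex 3) in at least 5 points at the end of the treatment".
- **Statistical Analysis.** For effectiveness, "the change in the IIEF-EF scale will be compared at the end of the treatment with the baseline score for each of the arms", with parametric tests if the "data present a normal distribution, or nonparametric tests otherwise". The section states no null value, no margin and no interval for the IIEF-EF difference. The only confidence interval it names is for the EHS relative risk.

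**The concern.** The two hypotheses do not meet. Ho covers a difference of exactly 0 and Ha covers 5 or more, so a true gain of, say, 3 points falls under neither. The primary outcome makes this worse: an outcome should be a quantity to estimate, and this one has a success threshold built in.

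The planned test can reject Ho, but rejection supports a difference above zero and not the 5 points written into Ha. The Sample size section calls 5 points the clinically relevant gain. A report that moved from a significant p-value to Ha as worded would therefore claim a clinically relevant effect that the test had not shown. Nothing in the Statistical Analysis section guards against that step.

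**Working it through.** **Inputs.** From Sample size: difference 5, SD 8 (read here as the SD of change in each arm), power 80%, 33 per arm. The 97.5% one-tailed level is read as one-sided 0.025. One-sided 0.05 is run as well, for the reason in step 1. Steps 2 to 4 assume normal data and, in steps 2 and 3, a two-sample t-test at a single look.

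**1. Which null gives the plan's 33?** With a null of 0 and a true difference of 5, the normal approximation is n = 2 × [SD × (z for alpha + z for power) / 5]².

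- One-sided 0.025: 2 × [8 × (1.960 + 0.842) / 5]² = 40.2, so 41 per arm (42 with the t-distribution).
- One-sided 0.05: 2 × [8 × (1.645 + 0.842) / 5]² = 31.7, so 32 per arm (33 with the t-distribution).

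So 33 is reproduced only at one-sided 0.05. That mismatch with the stated level is a separate matter. What counts here is the null. With a null of 5 and a true difference of 5, the numerator is unchanged but the distance to detect is 5 − 5 = 0. Power then equals alpha at any n, and no finite sample size exists. The 33 cannot come from a 5-point margin.

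**2. Smallest observed difference that rejects Ho.** SE = 8 × √(2/33) = 1.969, with 64 degrees of freedom.

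- One-sided 0.025: 1.998 × 1.969 = 3.93 points.
- One-sided 0.05: 1.669 × 1.969 = 3.29 points.

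With all 40 per arm analysed, SE = 8 × √(2/40) = 1.789 and the thresholds are 3.56 and 2.98. At 33 per arm and 0.025 the threshold stays below 5 for any SD up to 5 / (1.998 × √(2/33)) = 10.2.

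**3. How often Ho is rejected when the true gain is below 5** (noncentral t, noncentrality = true gain / 1.969, 33 per arm):

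| True gain | One-sided 0.025 | One-sided 0.05 |
|---|---|---|
| 2 | 17% | 26% |
| 3 | 32% | 45% |
| 4 | 52% | 64% |

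A Mann-Whitney test on simulated normal data (20,000 runs, one-sided 0.025) gives 16%, 31% and 49%, so the choice between parametric and nonparametric tests makes little difference.

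**4. A second reading of the primary outcome.** Suppose success needs significance and also an observed difference of at least 5. Because 5 exceeds both thresholds in step 2, the observed-difference condition almost always decides. Its probability is 1 − Φ((5 − true gain) / 1.969):

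- True gain 2: 1 − Φ(1.523) = 6%.
- True gain 3: 1 − Φ(1.016) = 16% (15.5% before rounding).
- True gain 4: 1 − Φ(0.508) = 31%.

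**The case against.** The strongest reply is that 5 points is simply the planning difference. The Sample size section uses it that way, alongside power and SD, and writing the design difference into Ha is a common shorthand. This is probably what was meant, and it stands: the underlying test is a conventional superiority test. It does not remove the fault, because Ha and the primary outcome still state something that this test does not establish.

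Some stronger readings are tempting, but the documents do not support them.

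- *The plan will report any significant result as a gain of at least 5 points.* No section says so. The primary objective speaks of an increase in the average score with no 5-point condition, and the analysis section has no rule that turns significance into that claim. The rates in step 3 describe one possible way of reporting. The rates in step 4 describe another, and are well below them.
- *The provision for placebo-arm patients contradicts the hypotheses.* The Techniques section makes it depend on a difference of unstated size. That fits the zero null, and it fits the hypotheses as reworded below.
- *The claim should be barred unless the lower confidence limit reaches 5.* At 33 per arm and one-sided 0.025 this needs an observed difference of 5 + 3.93 = 8.93. It would allow the claim in only 2.5% of trials if the true gain were exactly 5, the value planned for. Such a rule is a debatable choice and is not needed to remove the contradiction.

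It is also fair to say that the Statistical Analysis sentence, read literally, compares each arm with its own baseline. The hypotheses, and a later mention of comparison between groups, point to a between-arm test, which the arithmetic above assumes.

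**Conclusion.** The concern holds as a mismatch between the stated hypothesis and outcome and the test that serves them. It does not show that the test is invalid, and it gives no reason to change the sample size. The zero null follows from the wording of Ho and from the sample-size arithmetic. The analysis section does not state it.

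Rejection can occur on an observed gain of 3.9 points (one-sided 0.025) or 3.3 (one-sided 0.05), both short of 5, and this direction survives either reading of alpha and either 33 or 40 analysed per arm. How often an unsupported claim of at least 5 points would follow depends on the reporting rule, which the plan leaves open. At true gains of 2 to 4, it ranges from about 6% to 31% if an observed 5 points is also required, and from 17% to 64% if significance alone is enough, across the two alpha levels. These figures rest on SD 8, normal data and 33 per arm. The interim analysis at 60% of patients is not modelled.

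This should be corrected, because it governs what the trial may conclude and costs almost nothing to repair.

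**What to change.** **Research hypothesis.** State Ho as a difference of 0 or less, and Ha as a difference above 0, in mean IIEF-EF change from baseline to the end of treatment, radial waves minus placebo.

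**Primary Outcome.** Define it as the between-arm difference in mean IIEF-EF change from baseline to the end of treatment. Keep 5 points only as the planning difference and the benchmark for clinical relevance.

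**Statistical Analysis.** Say explicitly that the change is compared between arms. Add that the mean difference will be reported with a confidence interval matching the level of the test (two-sided 95% for one-sided 0.025, two-sided 90% for one-sided 0.05), also when a nonparametric test is used. Interpret the interval against 5 points, so that a significant test alone is not described as a gain of at least 5.

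**Cost.** A few sentences change; the test, sample size and data collection do not. The downside is that a significant result on its own no longer supports a claim of at least 5 points. If a rank test is used, it and the interval for the mean difference can also disagree near the threshold.

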 impulses in the perineal area.
- Arm 2 (Standard treatment (oral sildenafil) + Placebo therapy): Sildenafil according to the patient's degree of affectation + 6 sessions of placebo therapy. There will be a weekly session of placebo wave therapy, using the respective device to prevent the patient from receiving the radial wave. The same parameters of the "real" therapy will be used: 6000 pulses at 2.6 bar, with a frequency of 17 Hz; in all radial wave sessions, 4000 impulses will be distributed in the body of the penis in scanning technique and 2000 impulses in the perineal area.

Measurements will be made of the EHS and IIEF-EF scale scores, of the use of medication and of the possible adverse events of the therapy, at the beginning and end of the treatment, and one month after the therapies are finished.

Expected impact: Knowing the effectiveness and safety of radial waves for the treatment of erectile dysfunction will allow having a scientific basis for new treatment alternatives for men with this disease.

Introduction

Erectile dysfunction (ED) is defined as the persistent inability to reach and / or maintain an erection sufficient to allow a satisfactory sexual relationship (1). Epidemiological information on ED shows that it is a condition that has a high prevalence and incidence worldwide and that mainly affects men over 40 years of age (2). The prevalence of ED in the general population of men under 40 years of age is approximately between 1% and 10% (3). Both prevalence and severity increase with age, in men between 60 and 69 years of age, the prevalence of erectile dysfunction increases from 20% to 40%, and this range can increase from 50% to 100% in men between 70 and 80 years old (3-6).

Currently, there are different pharmacological and non-pharmacological treatments for erectile dysfunction, among which are the administration of medicines for oral use, intracavernous and intraurethral, lifestyle modification, vacuum devices, psychotherapy, extracorporeal therapy with low intensity shock waves (Li-ESWT), vascular surgery for selected cases, and alternative therapies (7-14).

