It will be determined by the presence of adverse events. These will be evaluated at the end of each of the therapies and a month of follow-up. This variable will be dichotomous as the presence or absence of adverse events. Additionally the type of adverse event and the degree of severity will be recorded.

Randomization

The assignment of patients to the treatment arms will be done with the method of randomization by balanced blocks of unequal cells. The assignment of the treatment will be centralized, so once the patient agrees to participate in the study and signs the informed consent, an email should be sent to the research center ([contact]) who will only inform the therapist which is the group (intervention or control) that corresponds to the patient.

To conceal the assignment sealed opaque envelopes will be used, this envelope will be opened once the request is generated in each center, after the patient has voluntarily accepted to participate in the study and the informed consent process has been carried out with signature of the written document.

Neither the patient, the attending physician, nor the professional who applies the questionnaires will know the group to which the patient was assigned.

Techniques, procedures, data collection and processing

The subjects who attend consultation for erectile dysfunction at the Boston Medical Group clinics in Bogotá (Colombia) and Lima (Peru), will be treated as usual according to the institutional management protocols and screened to determine if they meet the eligibility criteria. If so, they will be invited to participate in the research project and the informed consent process will be carried out in which the objectives, risks, benefits, procedures and other relevant research data will be explained.

Once the patient has voluntarily accepted to participate in the study and the informed consent document has been signed, an email will be generated to the research center to request the group to which the patient will be assigned.

A baseline measurement of the IIEF-EF and the EHS will be made before starting the intervention; In addition, the AMS questionnaire should be completed to rule out hypogonadism. Once the treatment is completed, patients must complete the IIEF-EF and EHS scales in the last treatment session. In this same session, the patient will be evaluated for adverse events; later, they will have

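### Sildenafil use before baseline is left open, which may cost the IIEF-EF comparison some precision, and the sildenafil-use outcome has no stated reference level

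*Combined protocol and SAP*

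**What the plan says.** All references are to the combined protocol and SAP.

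- **Eligibility (Inclusion and Exclusion criteria).** An IIEF-EF score of 11 to 21 is required. None of the 4 inclusion and 14 exclusion criteria mentions earlier use of sildenafil or a similar drug, and no wash-out or run-in is described.
- **Baseline (Techniques, procedures, data collection and processing).** Candidates are clinic attenders managed under the usual institutional protocols. "A baseline measurement of the IIEF-EF and the EHS will be made before starting the intervention"; nothing is said about sildenafil status at that measurement.
- **Treatment (Interventions).** In both arms, "During the period of therapy application, patients will receive oral treatment with sildenafil". Footnotes call this the standard treatment.
- **Sample size.** "Assuming that the placebo plus drug group has an average change in the score of the IFE-EF scale of 5 points", and "the new wave therapy must have an additional change of at least 5 points to be considered clinically relevant".
- **Medication record (Abstract).** Measurements are to be made "of the use of medication and of the possible adverse events of the therapy, at the beginning and end of the treatment", and again at one month.
- **Analysis (Statistical Analysis).** The IIEF-EF change is compared with a parametric or nonparametric test, with no covariate named. Regression models with covariates come in addition; comorbidities and other treatments are given as examples. For sildenafil, "The percentage of patients that decrease or discontinue the use of sildenafil in each group will be estimated", and the groups are compared by chi-square. Neither a reference level nor a restriction to users is given.

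**The concern.** A man not taking sildenafil at baseline would be scored off the drug at entry and on it at the end of treatment, so his change includes the effect of starting it. A man already taking it could be scored on the drug both times, and his change would not include that effect. If both kinds enrol, the same change score measures two things. The spread between the two kinds is noise in the main test, and the assumed control-arm change of 5 points depends on an unstated mix.

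The sildenafil-use outcome has a related gap. A reduction has to be measured from something. Counted from use before entry, a man who was not using sildenafil can only be a non-event, and every such man pulls both percentages and their difference towards zero. Counted from the dose at the start of therapy, all men can reduce. Two analysts could report different answers to secondary objective 3 from the same data.

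**Working it through.** **Inputs from the Sample size section.** Difference 5 points; "with a standard deviation of 8 points"; "for a power of 80% and a one-tailed level of significance of 97.5" per cent, read here as one-sided 0.025; 33 per group before losses and 40 after.

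**Inputs not in the documents (assumed).** Share of starters p: 10% to 50%. Results are the same for p and 1 - p, so this also covers 50% to 90%. Effect of starting sildenafil on the change score, S: 3 or 5 points, with 8 as an extreme. Share of users who reduce sildenafil: 50% v 20%, or 40% v 20%.

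**1. The plan's own figure.** n per group = 2(z_alpha + z_beta)² SD²/difference².
- One-sided 0.025: 2 × (1.960 + 0.842)² × 64/25 = 40.2, so 41 (42 by t-test).
- One-sided 0.05: 2 × (1.645 + 0.842)² × 64/25 = 31.7, so 32 (33 by t-test).

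The stated 33 therefore matches a one-sided 5% test, not 2.5%. That is a separate matter. Here it only sets the starting point: 33 per group at one-sided 0.025 gives 71% power by t-test.

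**2. Gain from adjusting for entry use.** A mix of starters and prior users adds p(1 - p)S² to the variance of the change. If the planned variance of 64 already contains it, adjustment leaves SD = sqrt(64 - p(1 - p)S²). The small loss of degrees of freedom is ignored.

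| S | p | p(1 - p)S² | SD after adjustment | Power, 33 per arm |
|---|---|---|---|---|
| none | - | 0 | 8.00 | 71% |
| 3 | 10% | 0.81 | 7.95 | 71% |
| 3 | 50% | 2.25 | 7.86 | 72% |
| 5 | 10% | 2.25 | 7.86 | 72% |
| 5 | 50% | 6.25 | 7.60 | 75% |
| 8 | 50% | 16.00 | 6.93 | 82% |

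If SD 8 instead holds within each kind of man, the unadjusted SD at p = 50%, S = 5 is sqrt(64 + 6.25) = 8.38. Power is then 67%, and adjustment restores 71%. Any further gain from adjusting for baseline IIEF-EF is not counted; it depends on a correlation that the documents do not give.

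**3. Chance imbalance is the same cost, not a second one.** At p = 50%, S = 5 and 40 per arm, one standard error of imbalance moves the arm difference by 5 × sqrt(2 × 0.25/40) = 0.56 points. The standard error of the difference is 8 × sqrt(2/40) = 1.79 unadjusted and 7.60 × sqrt(2/40) = 1.70 adjusted, and sqrt(1.79² - 1.70²) = 0.56.

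**4. Sildenafil use, if the reference is pre-entry use.** With half the men non-users at entry, 50% v 20% among users becomes 25% v 10% over everyone, and 40% v 20% becomes 20% v 10%. Two-sided 0.05 power is Phi[(d - 1.96 SE0)/SE1], with SE0 pooled and SE1 unpooled. For 25% v 10% at 40 per arm: (0.15 - 1.96 × 0.0850)/0.0833 = -0.20, which gives 42%. For 50% v 20% at 20 per arm: (0.30 - 1.96 × 0.1508)/0.1432 = 0.03, which gives 51%.

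| True rates among users | Everyone, 40 per arm | Users only, 20 per arm |
|---|---|---|
| 50% v 20% | 25% v 10%, power 42% | 50% v 20%, power 51% |
| 40% v 20% | 20% v 10%, power 24% | 40% v 20%, power 28% |

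If the reference is the dose at the start of therapy, every man is a user and this dilution does not arise.

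**The case against.** The strongest reply is that the mix is allowed, not shown. The documents fit a trial in which nearly every man starts sildenafil at entry, as the 5-point control change might suggest, or one in which nearly every man already takes it. In either case the effect is close to nil. Randomisation balances the mix in expectation. Adjusted models are already planned with an open list of covariates. And since every man receives sildenafil during therapy, a reference set at the start of therapy lets every man reduce.

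Much of this stands, and it rules out several stronger readings that a reader might infer:
- That two kinds of men are in fact mixed. No section says how many use sildenafil at entry.
- That the arm comparison is biased. Nothing in the documents makes the mix differ systematically between arms.
- That non-users at entry can never show a fall. This holds only under one of two possible reference levels.
- That the plan has no adjustment. It has supplementary models, although they name neither entry sildenafil use nor baseline IIEF-EF.
- That power on the sildenafil outcome is cut from 82% to 42%. The 82% is for 50% v 20% with 40 users per arm, a population that no change of analysis can create. The available gain is from 42% to 51%.

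What the reply does not remove is that the main test is unadjusted as written, the covariates of the supplementary models are left open, and the reference level is missing.

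**Conclusion.** The point holds as a modest loss of precision and a gap in definition. Sildenafil use before baseline is neither restricted nor standardised, so the IIEF-EF change may include the effect of starting the drug in some men only. With 10-50% starters and a 3- to 5-point starting effect, adjusting for entry use raises power at 33 per arm from 71% to 71-75%. An 8-point effect in half the men would take it to 82%, which is the upper end of what was examined. These figures rest on assumed shares and effects; if nearly all men are of one kind, the gain is negligible.

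For sildenafil use, the undefined reference level is the more substantial part, because it decides what is being estimated. Under a pre-entry reference with half the men non-users, the reported percentages and their difference are half the true ones among users. Under a start-of-therapy reference there is no such dilution.

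**What to change.** 1. **Main IIEF-EF comparison.** At end of treatment and at one month, make the between-arm comparison an ANCOVA adjusted for sildenafil use at entry (yes/no) and baseline IIEF-EF, in place of the unadjusted test of change, and do not leave this adjustment to the supplementary models.
2. **Sildenafil-use outcome.** State in Statistical Analysis the level from which a reduction or stop is counted. If it is pre-entry use, compare the arms among men using sildenafil at entry, and report men starting at entry separately, from their first prescribed dose.
3. **Data.** Confirm that the medication record at the beginning captures use before entry. The baseline list in Techniques, procedures, data collection and processing names only the IIEF-EF, the EHS and the AMS questionnaire. If the record starts with the sildenafil given in the trial, one further baseline item is needed.

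The cost is otherwise wording; no dose, schedule or eligibility rule changes. The downside is a smaller denominator for one secondary comparison. Under the assumptions above, power is still slightly higher than over everyone (51% v 42%, or 28% v 24%), but low either way.
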